7.1 Inclusion Criteria

People must meet all the following inclusion criteria to be eligible for inclusion in the study:

- The cohort for the endpoint analysis will consist of all adults and adolescents (aged 13+) contributing to OPCR during the study period.

- The cohort for the lifetime risk analysis will consist of all people contributing to OPCRCD during the study period.
- The vitiligo cohort consists of people newly diagnosed with vitiligo at any point during the study period.

7.2 Exclusion Criteria

People meeting any of the following criteria will not be included in the study:

- People with the alternative non-vitiligo diagnoses (other hypopigmenting conditions).
- People with vitiligo diagnosis within 6 months of practice registration.
- People without vitiligo with less than 1 year of follow up within the dataset.
- People over the age of 95 (for those reaching age 95 during the follow up period, follow up was censored at age 95).

People who have opted out of record sharing are not included (approximately 1.8% of the adult population).

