4.5 Secondary Endpoints

Objective	Endpoints
2	Mental health condition outcomes will be assessed up to two years post-vitiligo diagnosis, including history of prior mental health condition and will comprise of depression (record of any depressive episodes and/or major recurrent depression diagnosis) and anxiety disorders, defined by the International Statistical Classification of Diseases and Related Health Problems 10th Revision (ICD10) classification, and identified using algorithms validated for use in UK primary care data (See previously published codes lists: (4))
3	Other mental health condition outcomes will be assessed up to two years post-vitiligo diagnosis and will comprise of parasuicide/suicide attempts, adjustment disorder and sleep disturbance, defined by the International Statistical Classification of Diseases and Related Health Problems 10th Revision (ICD10) classification, and identified using algorithms validated for use in UK primary care data (See previously published codes lists: (4))

4	Healthcare utilisation outcomes will comprise primary care visits, dermatology referrals, mental health referrals (including but not limited to those via IAPT; Improving Access to Psychological Therapies and psychiatric reviews) in the two years post-vitiligo diagnosis.
5	Unemployment in the two years post-vitiligo diagnosis will be identified using Read codes relating to unemployment recorded in the primary care record or the issuing of IB113 or ESA113 forms (See previously published codes lists: (4)). Time off work in the two years post-vitiligo diagnosis will be indicated by the issuing of Med 3 certification from primary care (Statement of Fitness for Work certification) (See previously published codes lists: (4)).

Table 2: Secondary endpoints.

5. General Study Design and Plan

The study will use retrospectively collected anonymised data from all eligible people contributing to the Optimum Patient Care Research Database (OPCRD)(5) at the date of data extraction. A matched-cohort design will be used for incident (and prevalent) vitiligo related healthcare utilisation, mental health conditions and work impacts. Lifetime risk will be calculated using adapted survival analysis to account for the competing risk of death and will be estimated for the population overall and separately in sociodemographic subgroups of interest.

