All adults and adolescents (aged 13+ for disparity objectives 2-5 inclusive) contributing to OPCRd during the study period (January 1, 2004 and December 31, 2020 inclusive). People who have opted out of record data sharing will not be included (approximately 1.8% of the adult population) and have not been uploaded to the OPCRd database.

Cumulative lifetime risk of vitiligo will be estimated (using the method described in the statistical methods below) using cases of incident vitiligo occurring during the observational study period (January 1, 2004 and December 31, 2020 inclusive). A matched-cohort design will be used for incident (and prevalent) vitiligo related mental health conditions, healthcare utilisation and work impacts. For all analyses, the overall result including both adults (aged 18+) and children (aged 13-17) will be published, with stratification by age, sex, deprivation and ethnicity.

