5.2 Total disease burden; cumulative lifetime risk

A cross sectional design (incidence) will be used to assess the total disease burden of vitiligo, stratified by sociodemographic groups.

5.3 Disparities in the impact of vitiligo on mental health, healthcare utilisation and work impact

A matched-cohort design will be used for incident (and prevalent) vitiligo related: Mental health conditions; work impact; healthcare utilisation.

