7.3 Matching Process

For objectives 2-5, controls for each vitiligo case will be identified from the pool of people without a vitiligo diagnosis registered in the OPCRCD database at the time of vitiligo diagnosis for the case. Vitiligo cases will be eligible as controls up until the date of their vitiligo diagnosis (at which date their follow-up will be censored if selected as a control).

Each case will be assigned an index date at the time of their vitiligo diagnosis. Corresponding controls assigned to each case will have the same index date.

Each individual with vitiligo will be matched at their index date with up to four unaffected controls. Controls cannot be diagnosed with vitiligo at the date of matching and will require at least one year of follow-up time to minimise the risk of a non-recorded existing diagnosis of vitiligo. Time-updated exact matching will be performed by age, sex, ethnicity and deprivation, selected from the pool of eligible people registered in the same GP practice.

If required, a combination of time-dependent propensity score matching and exact matching will be performed to create a baseline matched dataset.

The matching process is subject to change depending on the feasibility of the mentioned matching process during the initial exploration of the data. The produced baseline matched dataset will be used for all analyses for objective 2-5.

8. Statistical Analysis

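### Objective 1 has no common start of time at risk, and the unequal exclusions in section 7.2 can push lifetime risk down or up depending on the entry date used

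*Combined protocol and SAP*

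**What the plan says.** Section 7.2 opens with "People meeting any of the following criteria will not be included in the study" and makes no exception for Objective 1. Two of its bullets depend on whether a person is later found to have vitiligo:

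- For cases: "People with vitiligo diagnosis within 6 months of practice registration". No minimum follow-up is asked of them.
- For non-cases: "People without vitiligo with less than 1 year of follow up within the dataset".

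On the Objective 1 cohort, section 7.1 says: "The cohort for the lifetime risk analysis will consist of all people contributing to OPCRCD during the study period". Section 5 says that lifetime risk will be estimated "using cases of incident vitiligo occurring during the observational study period", which is 2004 to 2020. Section 5.2 describes the design thus: "A cross sectional design (incidence) will be used to assess the total disease burden of vitiligo". Section 5 says: "Lifetime risk will be calculated using adapted survival analysis to account for the competing risk of death". None of these gives the date on which an individual becomes at risk. Section 8.2 refers to two published lifetime-risk methods without restating their entry rule.

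A one-year rule appears again in section 7.3, for matched controls in Objectives 2-5, who "will require at least one year of follow-up time to minimise the risk of a non-recorded existing diagnosis of vitiligo". That is the only reason the plan gives for a one-year period.

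**The concern.** An incidence rate is sound when events and person-time are counted over the same interval for everyone. Here the case rule sets one interval, the non-case rule sets another, and the denominator has no stated start. Two separate effects follow.

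- **The 6-month case bar.** If the first 6 months after registration stay in the denominator while diagnoses in those months are removed, incidence is too low.
- **The one-year non-case rule.** Someone diagnosed at month 7 who leaves at month 8 is kept; an undiagnosed person who leaves or dies at month 8 is deleted. This selects on what happens after entry. It removes person-time but no cases, so it acts upwards.

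The primary output is cumulative risk to age 80, overall and by sex, ethnicity and deprivation. Two programmers working faithfully from this text could produce different levels. If the entry date is settled only after the data have been seen, that choice moves the primary estimate.

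**Working it through.** The plan states no figure to reproduce, so this is a model of what each reading would do.

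**Inputs from the documents:** the two rules (7.2) and a 17-year window (section 5).

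**Inputs assumed, because the documents give none:** a constant exit hazard L of 0.05, 0.10 or 0.20 a year; constant registrations into a stable open population; a rare event with constant hazard, so that the vitiligo rate cancels; and the start of person-time, taken in four ways.

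**Formulas** (one registration per year, follow-up counted from registration):

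- True person-time: 17/L.
- Countable cases, in proportion to time beyond 6 months: 17·exp(−L/2)/L.
- Estimated/true incidence = countable cases ÷ the person-time used as denominator.

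**Worked at L = 0.10.** True person-time is 17/0.10 = 170. Countable cases are proportional to 170 × exp(−0.05) = 170 × 0.95123 = 161.71.

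- *A: person-time from registration, both bullets applied.* The one-year rule deletes three pieces:
  - people who register in the first 16 years and leave within a year: 16 × [1 − (1+L)exp(−L)]/L = 16 × 0.04679 = 0.749
  - everyone who registers in the last year: [1 − (1 − exp(−L))/L]/L = 0.484
  - in-window time of people who registered in the year before 2004 and left within a year: ∫₀¹ L·exp(−Lt)·t²/2 dt = 0.015
  - These sum to 1.248, so the denominator is 168.75 and the ratio is 161.71/168.75 = 0.958.
- *B: person-time from registration, one-year bullet for matched controls only.* 161.71/170 = exp(−L/2) = 0.951.
- *C: person-time from 6 months for everyone, one-year bullet kept.* The rule removes only about 0.3 of 161.71, so the ratio is 1.002. It is exactly 1 if the bullet applies to controls only.
- *D: non-cases counted from 1 year, cases from 6 months.* 161.71/(170 × exp(−0.10)) = 161.71/153.82 = exp(L/2) = 1.051.

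| Reading | 5% exit | 10% exit | 20% exit |
|---|---|---|---|
| A | 0.978 | 0.958 | 0.926 |
| B | 0.975 | 0.951 | 0.905 |
| C | 1.001 | 1.002 | 1.006 |
| D | 1.025 | 1.051 | 1.105 |

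Comparing A with B separates the two effects: the 6-month bar produces the understatement, and the one-year rule takes part of it back.

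**Mostly long-registered population.** Suppose 80% of person-time comes from long-registered people whom neither rule touches. The ratio is (0.8 + 0.2e)/(0.8 + 0.2d), where e and d are the retained shares of events and denominator. At 10% exit:

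- A: (0.8 + 0.2 × 0.95123)/(0.8 + 0.2 × 0.99266) = 0.99025/0.99853 = 0.992.
- D: 0.99025/(0.8 + 0.2 × 0.90484) = 0.99025/0.98097 = 1.009.

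Across 5%, 10% and 20% exit, A is 0.996, 0.992 and 0.985, and D is 1.005, 1.009 and 1.018.

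**Sensitivity of A to the model.** Counting follow-up from 2004 instead of from registration gives 0.979, 0.961 and 0.930. If everyone registered evenly over 2004-2020, with no earlier stock, the understatement would be 6.7%, 8.0% and 10.4%.

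**Subgroups.** With equal turnover the error cancels in a ratio. For 20% against 10% exit, the false ratio is 0.9255/0.9583 = 0.966 under A and 1.105/1.051 = 1.051 under D. These shrink to 0.994 and 1.008 in the 80% long-registered mix.

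**Scale.** For a rare disease, cumulative risk moves nearly in proportion to incidence. Take 2% as an illustrative risk to age 80 (the top of the range in 3.1, which is a prevalence and is used here only for scale). At 10% exit it would read 2 × 0.958 = 1.92% under A and 2 × 1.051 = 2.10% under D.

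**The case against.** The best reply is that the one-year bullet simply restates the control rule of 7.3. Its only rationale concerns controls, people without vitiligo are a comparator group that Objective 1 does not have, and 7.1 gives Objective 1 its own cohort. That reading is quite possible, and it would remove the selection on later follow-up from the primary analysis. It does not supply an entry date, however. If person-time still ran from registration, the understatement would be slightly larger (B rather than A).

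The second reply is that the cited methods papers may define entry. They may, and this cannot be judged from the documents. The 7.2 exclusions are this plan's own, though, and have to be reconciled with whatever entry date those papers use.

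Four stronger inferences are tempting, and the documents do not support them:

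- *That the plan, read literally, understates incidence by 2%, 4% and 7%.* This needs person-time to start at registration, which is written nowhere. Under D the sign reverses.
- *That the one-year rule causes the understatement.* It works the other way.
- *That subgroup comparisons will be distorted.* This happens only if turnover differs between subgroups, and the documents give no turnover data.
- *That the error is several standard errors wide, judged against 8,000 cases.* Section 6 gives that figure for anxiety and depression. No case count is given for Objective 1.

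**Conclusion.** The point stands as a gap in specification that can bias the primary estimate. Section 7.2 applies unequal rules by later vitiligo status to the whole study, and nothing in the text gives cases and non-cases the same start of time at risk. At 5-20% annual exit in a stable open population, the level of incidence could be about 2-7% low with both bullets applied and person-time from registration, 2.5-9.5% low without the one-year bullet, essentially right with a 6-month start for all, or 2.5-10.5% high with a 1-year start for non-cases only. If most person-time is long-registered, the errors are much smaller: 0.4-1.5% low under A and 0.5-1.8% high under D.

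The unequal rules and the missing date can be read directly from the text. The direction and size rest on assumed turnover and an assumed entry date, so confidence in any one percentage is limited. The main exposure is the level of lifetime risk, less so the contrasts between subgroups. It should be settled before analysis.

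**What to change.** For Objective 1, replace the two bullets in 7.2 with one rule, for example:

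*For every person, time at risk starts at the later of 1 January 2004 and 6 months after practice registration; people registered at birth enter at birth. Anyone with a vitiligo code before that date is excluded. Events and person-time are counted from the same start, and no minimum later follow-up is required.*

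Six months keeps the plan's existing case rule; any common period would remove the bias. State in 8.2 that this entry rule applies when the cited methods are used. Add to 8.4 a repeat of Objective 1 with 12 months in place of 6.

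Limit the one-year bullet to matched controls, place it in 7.3, and say there that it means registration before the index date. Giving cases and controls the same period in 7.3 is optional and not needed for this point.

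The cost is SAP wording and entry-date code. The main rule loses no further cases. In the stable open population, the 12-month sensitivity analysis loses 1 − exp(−L/2) of them, about 2.5%, 5% and 9.5% at 5%, 10% and 20% exit. That raises its standard errors by exp(L/4) − 1, about 1.3%, 2.5% and 5.1%.

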7.3 Matching Process

For objectives 2-5, controls for each vitiligo case will be identified from the pool of people without a vitiligo diagnosis registered in the OPCRCD database at the time of vitiligo diagnosis for the case. Vitiligo cases will be eligible as controls up until the date of their vitiligo diagnosis (at which date their follow-up will be censored if selected as a control).

Each case will be assigned an index date at the time of their vitiligo diagnosis. Corresponding controls assigned to each case will have the same index date.

Each individual with vitiligo will be matched at their index date with up to four unaffected controls. Controls cannot be diagnosed with vitiligo at the date of matching and will require at least one year of follow-up time to minimise the risk of a non-recorded existing diagnosis of vitiligo. Time-updated exact matching will be performed by age, sex, ethnicity and deprivation, selected from the pool of eligible people registered in the same GP practice.

If required, a combination of time-dependent propensity score matching and exact matching will be performed to create a baseline matched dataset.

The matching process is subject to change depending on the feasibility of the mentioned matching process during the initial exploration of the data. The produced baseline matched dataset will be used for all analyses for objective 2-5.

8. Statistical Analysis

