8.3 Secondary Endpoint Analysis

Objective 2

Anxiety and depression outcomes will be captured if occurring prior to, or within two years of, an individuals' study index date. Binary outcome logistic regression model outputs will be used to compare the burden of anxiety and depression in vitiligo cases compared to matched controls. Furthermore, additional analyses for new onset anxiety and depression outcomes will be conducted, excluding people with a previous record of the respective mental health condition. Anxiety and depression outcomes will be defined by the first occurrence of a relevant code in the primary care record up to two years post index-date. Cox proportional hazards regression will be used to estimate the excess risk of anxiety and depression outcomes in vitiligo cases versus controls. Results will be described as hazard ratios.

Objective 3

Parasuicide/suicide attempts will be defined by the first occurrence of a relevant code in the primary care record up to two years post index-date. People with a previous record of parasuicide/suicide attempt will be excluded from the calculations. Cox proportional hazards regression will be used to estimate the excess risk of parasuicide/suicide attempts in vitiligo cases versus matched controls. Results will be described as hazard ratios.

Adjustment disorder and sleep disturbance will be defined by the first occurrence of a relevant code in the primary care record up to two years post index-date. People with a previous record of the adjustment disorder will be excluded from the from the adjustment disorder endpoint analysis. Cox proportional hazards regression will be used to estimate the excess risk of the relevant condition in vitiligo cases versus matched controls. Results will be described as hazard ratios.

Objective 4

Dermatology referral and mental health referral or reviews will be defined by the first occurrence of a relevant code in the primary care record up to two years post index date. Cox proportional hazards regression will be used to estimate the excess risk of these outcomes in vitiligo cases versus matched controls.

For primary care encounters reviews, defined as a rate of encounters within two years after the index date, will be compared using generalised linear models with time-at-risk as an offset. Results will be described as incidence rate ratios.

Objective 5

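### Minimum record time differs between cases and controls, runs on different clocks and is not defined as pre-index, so earlier anxiety and depression may be captured differently in the two groups

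*Combined protocol and SAP*

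**What the plan says.** Section 7.2 has two separate entry rules. It removes "People with vitiligo diagnosis within 6 months of practice registration", and it removes "People without vitiligo with less than 1 year of follow up within the dataset". The first clock starts at practice registration; the second counts time in the dataset.

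Section 7.3 repeats the one-year rule for controls and gives its purpose: they "will require at least one year of follow-up time to minimise the risk of a non-recorded existing diagnosis of vitiligo". No such rule is set for cases. On the index date it says: "Corresponding controls assigned to each case will have the same index date". On the matching variables: "Time-updated exact matching will be performed by age, sex, ethnicity and deprivation", within the same practice. Length of registration is not among them.

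In section 8.3 the Objective 2 burden outcome has no fixed look-back: anxiety and depression are "captured if occurring prior to, or within two years of" the index date. The new-onset analyses are run "excluding people with a previous record of the respective mental health condition", so they also depend on how much history is visible.

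**The concern.** If a year of record is wanted before a control is accepted as free of existing vitiligo, the same worry applies to a case whose first code is taken as onset. The plan gives no reason for allowing cases half that time.

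A case diagnosed seven months after joining a practice can enter. Read as a pre-index rule, the control requirement bars a control with an equally short record. The Objective 2 logistic model counts any earlier code, so a shorter record in some cases could lower the case proportion with no true difference. The new-onset Cox model could err the other way: an old condition missed in a case and re-coded after index would count as new.

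Nothing else in the plan deals with this. Registration length is not in the adjustment sets of 8.1 and is not mentioned in the limitations of section 9. Of the sensitivity analyses in 8.4, one requires controls to have had an encounter in the year before index, one extends the outcome period and one recodes missing ethnicity. None equalises look-back.

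**Working it through.** **The plan's own figures.** The plan gives no number for look-back. Its only related figures are the detectable differences in section 6: 1.11 points for anxiety and 1.12 for depression with 8,000 cases. With the Kelsey formula, n = (z_a + z_b)² × p̄(1 − p̄)(k + 1)/(d²k), two-sided, 80% power and k = 4 controls per case, 8,000 cases give d = 1.26 points at 15% and 1.06 at 10%. The stated pair was not reproduced under any single setting tried, so it is not used as a benchmark here. The point does not depend on it.

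**Model for reading A: the year is pre-index and only in-practice history is held.** All rates are assumptions; the documents give none.
- h = yearly exit from a practice, 0.05 to 0.20.
- r = yearly rate of a first anxiety or depression code, 0.01 to 0.03, the same in both groups (no true effect).
- Look-back = L + an exponential time with rate h, where L = 0.5 years for cases and 1 year for controls. Two years of follow-up are complete.

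P(any record by two years) = 1 − exp(−r(L + 2)) × h/(h + r).

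Example with h = 0.10, r = 0.02:
- Cases: 1 − exp(−0.05) × 0.8333 = 20.73%.
- Controls: 1 − exp(−0.06) × 0.8333 = 21.52%.
- Difference −0.79 points; OR = (0.2073/0.7927)/(0.2152/0.7848) = 0.954.

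| h | r | Cases % | Controls % | Difference (points) | OR |
|---|---|---|---|---|---|
| 0.05 | 0.01 | 18.72 | 19.13 | −0.41 | 0.974 |
| 0.05 | 0.03 | 42.02 | 42.88 | −0.86 | 0.965 |
| 0.10 | 0.01 | 11.34 | 11.78 | −0.44 | 0.958 |
| 0.10 | 0.03 | 28.64 | 29.70 | −1.06 | 0.950 |
| 0.20 | 0.01 | 7.11 | 7.58 | −0.46 | 0.934 |
| 0.20 | 0.02 | 13.52 | 14.39 | −0.86 | 0.931 |
| 0.20 | 0.03 | 19.33 | 20.53 | −1.20 | 0.927 |

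The whole difference comes from cases diagnosed in months 6 to 12 after registration. Their share is 1 − exp(−0.5h): 2.5%, 4.9% and 9.5% at h = 0.05, 0.10 and 0.20.

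**A milder version of A.** Let a share s of cases have 6 to 12 months of record and miss a fraction m of the histories that their controls show. The difference is then −P × s × m. With s = 5% and m = 25%, it is −0.10 × 0.05 × 0.25 = −0.13 points for depression and −0.15 × 0.05 × 0.25 = −0.19 points for anxiety, with an OR of about 0.985 in each.

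**Reading B: the year may fall after index.** In the extreme, controls have no pre-index minimum (L = 0) and cases keep L = 0.5. The same formula gives ORs from 1.03 (h = 0.05, r = 0.01) to 1.08 (h = 0.20, r = 0.03). Controls would also be selected on future follow-up, which is a separate problem.

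**Reading C: earlier history is imported at registration.** Look-back then no longer depends on registration length, and the bias from this source is near zero.

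**The case against.** The strongest reply is that the look-back contrast rests on a reading the text does not settle. Neither 7.2 nor 7.3 says that the year precedes index, and both use follow-up elsewhere for time that is later censored. The stated purpose favours pre-index time but does not establish it. This stands, and it means no direction can be asserted.

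Section 5.4 describes the database as complete for coded primary care events, and 5.7.1 relies on first-ever codes and on diagnoses before the study period. That suggests earlier history may be visible, but the documents do not say how far a record reaches back before registration.

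The illustration also covers control proportions from 7.6% to 42.9%. Restricted to the 10 to 15% background in section 6, the same model gives 0.43 to 0.89 points. This stands too: the numbers show what is possible and do not estimate a bias.

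Four stronger inferences are tempting, and the documents do not support them:
- *Cases as a group have half a year less look-back.* Only the minimum differs; the half-year average follows from the exponential assumption.
- *The bias mimics a sociodemographic disparity through mobility.* Controls are matched within practice on age, sex, ethnicity and deprivation, the documents hold no mobility data, and moving the OR from 0.97 to 0.93 takes a fourfold difference in exit rate.
- *New cases are overstated by 2.5 to 9.5%.* This needs recording in months 6 to 12 to run at twice the long-run rate, which nothing in the plan supports, and it concerns Objective 1 incidence.
- *The plan holds that one year is needed to rule out vitiligo.* It says only that the year reduces a risk, and says so for controls.

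**Conclusion.** The concern holds as a risk of differential capture; a demonstrated bias is not shown. The plan itself establishes that the minimum record times are unequal, run on different clocks and are not tied to the index date; that the stated reason applies equally to cases; and that Objective 2 uses an open-ended look-back with no matching, adjustment or sensitivity analysis for registration length.

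The consequence depends on two things the plan leaves open: whether the year is pre-index, and whether history from before registration is held. Under reading A the burden OR is pulled down, to 0.93 to 0.97 on the assumed rates, while the new-onset HR may be pushed up, so the two Objective 2 analyses could diverge artificially. Under B the direction can reverse. Under C the effect is near zero. The effect is small in most scenarios, but the study sets out to describe differences between groups and the remedy is cheap, so the change should be made.

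**What to change.** In 7.3, for the matched cohort (Objectives 2 to 5), require at least 12 months of continuous registration before the index date for both cases and controls, with no requirement after index.

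An equal minimum does not by itself equalise an open-ended look-back. In 8.3, use the same look-back in both groups for the prior-record exclusions and for the Objective 2 burden outcome: a common fixed window, or matching or adjustment on prior registration time. State whether coded history from before registration is held. Keep the six-month case rule as a sensitivity analysis.

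The exclusions in 7.2 are study-wide. If the case rule there is also changed for Objective 1, start person-time at the same point; otherwise confine the change to the matched cohort.

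Cost: a wording change and the loss of cases diagnosed 6 to 12 months after registration. At assumed exit rates of 5 to 20% a year that is about 2.5 to 10%. Using the computed 2.47% and 9.52%, 8,000 × 0.0247 = 198 and 8,000 × 0.0952 = 762, leaving about 7,800 to 7,240 cases. At a fixed matching ratio the detectable difference grows by 1/√0.9753 to 1/√0.9048, or about 1 to 5%. A fixed window would also leave older history out of the burden outcome.
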